468 469 470 471 472 473 474 475 476 477	
 
Physical examination: including weight, blood pressure, etc.
 
Routine laboratory assessment: blood will be drawn to obtain values for the following tests: multichannel automated liver function tests, serum sodium, albumin, AFP, creatinine, and coagulation panels
 
Blood sample for NIDDK Biosample Repository
 
Quality of life interval assessments at 3, 6, and 12 months and annually thereafter
 
Liver MRI/contrast CT at Month 3 only.
 
Recipients of a DDLT from an HCV-antibody positive donor must have HCV genotyping done at 3 months post-transplant
 

478 479	Post-transplant Interval Assessments – HCV-infected Recipients:
480	In addition to the assessments listed above, HCV-infected recipients will undergo the following assessments at the following time points:

483	• Week 1, Month 1, Month 3, Year 1, 2, and 3: HCV RNA quantitative or qualitative
484	analysis
485	• Month 3, Year 1, 2 and 3: Liver biopsy
486	• Month 3, Year 1, 2 and 3: Tissue sample for NIDDK Biosample Repository
487	
488	Post-transplant Interval Assessments – Subjects with HCC:
489	
490	In addition to the assessments listed above for all recipients, recipients with HCC will
491	undergo the following assessments at Months 6, 12, 18 and 24:
492	
493	• Serum AFP (at month 18 in addition to AFP's done at interval assessments for all
494	recipients)
495	• Abdominal MRI/contrast CT: at months 6, 12 and 24 only.
496	
497	Subjects Showing Signs and Symptoms of Allograft Rejection:
498	
499	Subjects showing signs and symptoms of allograft rejection will undergo a liver biopsy
500	with analysis to confirm the diagnosis of rejection. A biopsy will be performed to
501	confirm each rejection episode. A tissue sample from these biopsies will also be sent for
502	storage at the NIDDK Biosample Repository.
503	
504	Post-Donation Assessments – Donors:
505	
506	The following assessments will be performed for donors at Week 1, and Months 1, 3, and
507	12, and annually thereafter until the study is complete or the donor reaches a study
508	endpoint or is lost to follow-up:
509	
510	• Routine laboratory assessment: blood will be drawn to obtain values for the
511	following tests: multichannel automated liver function tests, albumin, creatinine,
512	coagulation panels, white blood cell count, hemoglobin, ferritin, platelets, BUN
513	Blood sample for NIDDK Biosample Repository
514	• Liver MRI/contrast CT at month 3 only
515	• Quality of life assessment: limited to a pain survey at Week 1 and Month 1 for
516	donors. Donor and donor controls will undergo the full battery of QOL assessments
517	at Months 3, 12 and annually thereafter.
518	• Informed consent assessment (satisfaction with treatment): at Months 1, 3, and 12,
519	and annually thereafter
520	• Informed consent assessment (motivation): at Week 1, Months 3 and 12, and annually
521	thereafter.
522	• Donor controls will be asked to complete the QOL, Informed Consent and data
523	collections. No diagnostic, imaging or invasive procedures will be performed once
524	the decision not to donate has been made.
525	

## 4.1. Primary Aim 1: To quantify the impact of choosing LDLT on the candidate for transplantation

#### 528 4.1.1. Study Methods

529 Patients enter this study as candidates for transplantation, and will not necessarily 530 become recipients. Potential outcomes for these patients may include LDLT, DDLT, 531 withdrawal from the waiting list, or death on the waiting list. The entry point would be at 532 initial evaluation of a potential donor that includes history and physical examination at 533 the transplant center. Our preliminary data indicate that between one-third and two-thirds 534 of potential LDLT candidates will actually undergo LDLT. This leads us to expect that 535 enrollment of both donors and potential recipients at the time of donor history and 536 physical examination will generate a number of control recipients who wait for a DDLT, 537 as well as a cohort of potential donors who do not donate to generate a population of 538 recipient and donor controls roughly equal in number to the LDLT population.

539

540

#### 4.1.2. Participant Selection

- 541 See Section 4.
- 542 **4.1.3. Data Elements**
- 543 A. Potential Recipient Data Collection544 Pre-transplant
- 545 1. Recipient Study Enrollment
- 546 2. Listing and Transplant data
- 547 3. Recipient Demographic data
- 548 4. Recipient Condition at Enrollment
- 549 5. Recipient Condition at Listing
- 550 6. Recipient Hospitalization and Complication data
- 551

- 552 B. Recipient Data Collection
- 553 Transplant and post-transplant follow-up
- 554 1. Recipient Condition at Transplant
- 555 2. Recipient Intraoperative Data
  - 3. Recipient Post-Surgical Morbidity
- 557 4. Recipient Complication Severity
- 558 5. Recipient Hospitalization data
- 6. Recipient QOL Assessment (See Appendix C)
- 560 7. Recipient Survival
- 561
- 562 C. Potential Donor Data Collection
- 563 1. Donor Evaluation
- 564 2. Donor Demographic Form
- 565566 D. Donation and post-donation follow-up
- 567 1. Donor Intraoperative Data
- 568 2. Donor Post-Surgical Morbidity
- 569 3. Donor Hospitalization data

- 570 3. Donor QOL Assessment
- 571 4. Donor Survival

#### 572 **4.1.4. Sample Size and Power Calculations**

573 We will compare the survival experience between those who receive an LDLT and those considered for an LDLT but not receive one. Although the analysis will involve a fairly 574 575 complex method of matching LDLT recipients with sets of non-recipients, for the 576 purpose of power calculations, we will assume a much simpler 2-group design. For this 577 analysis, we will pool the patients from the Retrospective Study and the Cohort Study for 578 maximum power. We anticipate having at least 300 LDLT recipients and 500 non-LDLT 579 recipients from the Retrospective Study, and 360 LDLT and 710 non-LDLT from the 580 Cohort Study, for a total of 660 LDLT and 1210 non-LDLT recipient patients. Power 581 calculations are based on the (two-sided) logrank test, an exponential survival 582 distribution, approximately uniform accrual of patients for at least 7 years (from 1998) 583 with 3 additional years of follow-up, 1% loss to follow-up, and a significance level of 584 0.05. Assuming a one-year survival probability of 0.875 in the LDLT group, we have 585 90% power to detect as significant a one-year survival probability among non-recipients 586 lower than 0.85 or higher than 0.90.

[figure not shown]
#### 587 **4.1.5. Statistical Analysis**

588 A comparison of survival between LDLT recipients and those evaluated for LDLT but 589 not receiving a living donor organ will be made. The time origin for the survival analysis 590 will be the date of donor evaluation. A preliminary comparison of the death rates in each 591 group will be made using number of deaths divided by person-years at risk. For the LDLT group, time at risk will commence when the LDLT surgery is scheduled, and 592 593 terminate at death, end-of-study censoring, or cancellation of the surgery. For the non-LDLT group, time at risk will commence at donor evaluation and terminate at scheduling 594 595 of surgery, death, or end-of-study censoring; time at risk will also include the time 596 interval between cancellation of a surgery, death or end-of-study censoring. This analysis 597 estimates "overall" death rates, without considering changes in the risk of death over 598 time. The analysis also does not incorporate covariate effects. However, it will provide 599 a broad estimate of the potential benefit of LDLT.

600

601 A second analysis comparing these groups will use Cox regression, with the time origin 602 at the donor evaluation, and covariate adjustment for age, gender, race, calendar year of 603 initial evaluation, time on the waitlist, liver disease etiology and severity (including 604 MELD (Model for End stage Liver Disease) score or Status, as applicable), comorbidities 605 and other variables. The treatment strategies of LDLT versus no LDLT will be compared 606 using a time-dependent indicator covariate for LDLT transplantation. In particular, this 607 analysis will compare the risk of death at each time point after first donor evaluation for 608 those having received an LDLT prior to that point versus those who have not. This 609 analysis assumes that most candidates evaluated for LDLT either receive the transplant or 610 do not receive it due to problems with the donor. In particular, it assumes that non-611 progression to LDLT due to DDLT transplantation or because the recipient becomes too 612 sick to transplant is rare. Having many patients with non-progression to LDLT due to 613 declining condition would bias the comparison by having sicker people in the non-LDLT 614 group. These assumptions can be evaluated when the data are available.

- A third, more complicated analysis will be performed that has the advantage of avoiding 616 617 the assumptions mentioned above. This method will compare survival from the time of 618 LDLT surgery among LDLT recipients to sets of controls that were evaluated for LDLT, and were alive and eligible for transplant at the same time following donor evaluation as 619 620 the LDLT patient was when they received their transplant. This analysis will involve a 621 different set of controls for each LDLT patient, with many patients re-used in several 622 control sets. For a particular LDLT, a control group will be identified of all patients alive 623 and awaiting transplant at the time of that LDLT. The survival experience of that LDLT will be compared with that of its control group. This set of an LDLT and its control 624 625 group are illustrated in the figure below. 626
- 626
- 627
- 628

#### 629

630 Those people in that control group who subsequently receive an LDLT transplant are 631 censored from that control group, but initiate a new LDLT group with its own control group. For a new LDLT, the control group will be composed of many of the same people 632 who were in control groups for previous LDLTs, although some of the previous controls 633 634 may not be included due to death, having received a DDLT or LDLT transplant or 635 leaving the waitlist. Comparisons between each LDLT and its control group will then be 636 pooled in a single analysis using Cox regression. The Cox model will be stratified by the LDLT/control group set. Because many people will appear in multiple control sets, we 637 will use a robust variance estimate based on the sandwich estimator to provide statistical 638 639 adjustment for the re-use of controls in multiple control groups (4, 5). As a check on this 640 method of variance adjustment, bootstrap variance estimates will also be computed. Briefly, bootstrap variance estimates are computed by resampling from the data with 641 642 replacement, computing the effect estimate for each re-drawn sample, and calculating the 643 variance of the effect estimates obtained. Covariate adjustment will include all variables listed for adjustment in the first Cox model described above. An additional assumption 644

645 must be made for this analysis: that those members of a control group who receive an 646 LDLT (and are then censored from that control group) are not different in any systematic 647 way from those remaining in the control group with similar covariate values. This is 648 known as the assumption of random censoring. We can check to see if receipt of an 649 LDLT is predicted by known covariates, and can adjust for these covariates in the 650 survival analysis. We will not know if censoring is affected by unknown variables that 651 may bias the analysis. To assess the impact of the assumptions of the initial analysis 652 above [i.e., that most candidates evaluated for LDLT either receive the transplant or do 653 not receive it due to problems with the donor], we will compare the results from the first 654 and second methods. If a discrepancy is found, we will consider the results of the second 655 analysis to be freer of bias and thus preferable.

656

In both Cox analyses described above, variables will be checked to ensure that theproportional hazards assumption is met. If non-proportional hazards are detected,

- 659 particularly for the LDLT effect, they will be modeled using time-dependent covariates.
- 660 Interactions between covariates and the LDLT effect will be tested.
- 661

662 In addition, individual components of the process will also be analyzed. We will

663 separately estimate the distributions of time to death on the waitlist, time to transplant, 664 and time to death following DDLT. We will use these three distributions to estimate the 665 distribution of time to death for those not receiving a LDLT, confirming our combined 666 estimate with the one-step estimate obtained as described above. With these estimates in 667 place, we can then project the change in the overall survival distribution for specific 668 changes in each of the component distributions. For example, if the distribution of time 669 to transplant changes, say as a result of an increase in organ donations, then the effect of 670 this change on non-LDLT survival could be estimated.

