1232	of A2ALL transplant centers) to be 360 LDLT and 355 DDLT. We assume that 30% of
1233	waitlist patients have HCV, or approximately (0.30*360=) 108 LDLT and (0.30*355=)
1234	107 DDLT. All calculations below assume two-sided testing with a significance level of
1235	0.05.

- 1237 1. The primary endpoint upon which the study will be powered is histological severity of 1238 disease at 1 year. We base sample size calculations on a comparison of binomial 1239 proportions. If we assume that 10% of DDLT patients achieve the composite endpoint of 1240 (Ishak  $\geq$ 3, etc), we have 82% power to detect an increase in the LDLT proportion to 25%.
- 1240

1242 2. The secondary endpoints also capture rate of disease progression. If we assume 50%

1243 of DDLT patients will achieve the composite endpoint at 3 years, we will have 85%

1244 power to detect an increase in the LDLT proportion to 70%. Thus, based on dichotomous

1245 endpoints (progression or not), we can only detect a difference between LDLT and

- 1246 DDLT with high power only if the difference is at least 15-20%.
- 1247

1248 Alternatively, we can look at differences in fibrosis progression using a numeric scale.

1249 With an estimate of SD=0.25 for the yearly rate of increase in fibrosis score, we have

1250 82% power to detect an increase or decrease of 0.10 compared to 0.45 (DDLT)

- 1251 [Berenguer 2000 -- for DDLT 0.3-0.48/year on Desmet scale 0-4)]. Power will be
- 1252 greater to detect LDLT rates above 0.55 or below 0.35.
- 1253
- 1254

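### The Aim 1 rule for resolving discrepant results points by number to the wrong analysis: under the section's own labels the preferred model is the one that rests on the doubtful assumption

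*Protocol*

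**What the plan says.** Protocol section 4.1.5 describes three ways of comparing survival in Primary Aim 1.

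- It opens with crude deaths per person-years: "A preliminary comparison of the death rates in each" group. There is no covariate adjustment.
- Next comes a Cox model starting at donor evaluation, with a time-dependent indicator for LDLT: "A second analysis comparing these groups will use Cox regression, with the time origin". The section attaches a condition to this model: the "analysis assumes that most candidates evaluated for LDLT either receive the transplant or" miss it because of the donor. It adds that many patients dropping out through "declining condition would bias the comparison by having sicker people in the non-LDLT" group.
- Last comes a Cox model stratified by sets, each made up of one LDLT recipient and the patients still alive and awaiting transplant at that moment: "A third, more complicated analysis will be performed that has the advantage of avoiding" the assumptions just described.

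After noting that the control-set model needs random censoring, the section gives its rule. To judge the assumptions of what it now calls the initial analysis "above [i.e., that most candidates evaluated for LDLT either receive the transplant or do" not because of the donor, it will compare the first "and second methods. If a discrepancy is found, we will consider the results of the second" analysis to be less biased and so preferable.

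**The concern.** The ordinals in the rule do not match the ordinals used to introduce the analyses. The only analysis introduced as second is the time-dependent Cox model, which the section itself says can be biased against the non-LDLT group. The analysis designed to escape that bias is introduced as third, and the rule does not mention a third. An analyst who follows the numbering would prefer the time-dependent Cox result when results conflict, and could cite the protocol for doing so.

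This is the only sentence in section 4.1.5 that says which estimate prevails for Primary Aim 1 when analyses disagree. A rule of that kind should identify its methods without the reader having to work out which count is in use.

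**Working it through.** No figure is in dispute, so this is a check of labels against content within section 4.1.5.

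**Step 1. Each analysis, its label where introduced, and its assumption.**

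| Analysis | Label where introduced | Donor-problem assumption | Later labels in the section |
|---|---|---|---|
| Crude death rates | preliminary | not discussed | none |
| Time-dependent Cox | second | rests on it | first Cox model (in the covariate list for the control-set analysis); initial analysis (in the rule) |
| Control-set stratified Cox | third | said to avoid it | none by number, unless it is the rule's second analysis |

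The time-dependent Cox model thus carries up to three labels: second, first Cox and initial.

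**Step 2. The rule under the introductory labels.** The first method is the crude rates and the second is the time-dependent Cox model. The rule prefers the time-dependent Cox model, which is the one resting on the assumption. The comparison also cannot do its stated job. Crude rates and the time-dependent model differ in covariate adjustment, in whether death risk may change over time, and in when a patient moves into the LDLT group (surgery scheduled versus LDLT received). Neither is presented as removing candidates who miss LDLT through decline from the non-LDLT group. A difference between them would say little about the assumption, and the method said to avoid it is absent.

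**Step 3. The rule counting only Cox models.** The first method is the time-dependent Cox model and the second is the control-set model. The rule prefers the control-set model. The comparison sets an assumption-dependent model against one said to avoid the assumption, so it fits the stated purpose and the reason given for introducing the control-set analysis.

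**Step 4. Which count was meant.** Three pieces of text favour step 3:

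- The bracketed gloss ties the donor-problem assumption to the initial analysis, and that assumption was stated only for the time-dependent Cox model.
- The covariate list for the control-set analysis refers back to the time-dependent model as the first Cox model.
- The next paragraph, on proportional hazards, speaks of both Cox analyses.

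Against it stand the explicit introductions as second and third. Steps 2 and 3 give opposite preferred analyses.

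**The case against.** The strongest reply is that the rule explains itself. Its bracket identifies the initial analysis by its assumption, only the time-dependent Cox model has that assumption, and crude rates are called preliminary, never first. A careful reader would conclude that the control-set model is preferred. That stands as evidence of intent. A reader might infer that the protocol knowingly chooses a biased estimate, and the text does not support that. The reply does not remove the contradiction, because the intent has to be inferred against explicit labels a few paragraphs earlier.

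Three stronger readings are tempting and should not be made.

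- *The assumption already fails on the plan's own numbers.* Section 4.5.4 expects the number "of A2ALL transplant centers) to be 360 LDLT and 355 DDLT", and section 4 says that at least half of candidates go on to wait for DDLT. But sections 4 and 4.2.2 allow DDLT controls who never had a donor evaluated, and no breakdown is given. A candidate who waits for DDLT because the donor was unsuitable also satisfies the assumption. Section 4.1.5 says it will be evaluated when data are available.
- *The bias can be sized.* The protocol gives neither the share of candidates too sick to proceed nor their excess hazard, and the model adjusts for disease severity. Any figure would come from invented inputs.
- *The undefined discrepancy permits a choice after the results are seen.* The preferred method is meant to be fixed in advance, and a threshold is detail that a statistical analysis plan commonly supplies.

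**Conclusion.** The contradiction holds as a labelling error in a decision rule. By the numbering in section 4.1.5, the rule prefers the time-dependent Cox model and omits the control-set model; by the bracket and the references to the Cox models, it prefers the control-set model. The second meaning is very probably intended, but the text does not settle it.

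The consequence is which of two hazard ratios is preferred for Primary Aim 1 when they differ. Its numerical size is unknown, and if the two models agree the error has little effect. The conclusion rests only on the wording of section 4.1.5. It does not depend on whether the donor-problem assumption is true, and it does not show that the control-set analysis is free of bias: the section says that model needs random censoring, which cannot be checked for unmeasured variables.

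**What to change.** Replace the ordinals in the rule with method names, for example: 'We will compare the time-dependent Cox analysis with the control-set stratified Cox analysis. If they differ, the control-set analysis will be considered freer of the bias from non-progression to LDLT for reasons other than the donor, and will be preferred.' Use the same names in place of initial analysis and first Cox model elsewhere in section 4.1.5.

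Keep the random-censoring caveat next to the rule, so that the preference is seen to concern one source of bias. It is not necessary to declare the control-set analysis primary regardless of the other results; that would go beyond correcting the error.

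The cost is one rewritten sentence and a few consistent labels, with no new data or analysis. It should be done before the Aim 1 results are seen.

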# 4.2. Primary Aim 2: To characterize the differences between LDLT and DDLT in terms of post-transplant outcomes including patient and graft survival, surgical morbidity, resource utilization and QOL on the recipient of a transplant.

675 **4.2.1. Study Methods** 

676 This analysis will compare LDLT to contemporaneous deceased donor transplants 677 beginning at the time of transplantation. The LD group would be all LD transplantations. We anticipate that the clinical comparisons between LDLT and DDLT recipients can be 678 679 satisfactorily fulfilled with comparable numbers of transplants in each group for 1:1 680 statistical analysis. Because, by definition, DDLT candidates who are enrolled will not 681 be transplanted immediately, no DDLT controls will be available in the cohort until DD 682 livers become available, as their clinical condition declines over time. The need for 683 contemporaneous DD controls may need to be met by the enrollment of recipients who 684 may or may not have been considered for LD in the past. Since the ratio of LDLT:DDLT 685 among our study centers varies from 1:100 to 1:3, there is a risk of selection bias unless 686 DD controls are selected by some standardized approach. The first choice for DD controls will be patients from the A2ALL Retrospective Study who have not yet received 687 688 DDLT. Ideally, DDLT transplants will be enrolled in a time frame comparable to the 689 LDLT with whom they will be compared.

